## 1. Introduction and Background

Within the Norris Cotton Cancer Center's (NCCC) catchment area of VT and NH, we have higher HPV vaccination rates than many other states, but are experiencing plateauing rates among females, and the male rates continue to lag behind female rates. Both the VT State Cancer Plan 2016-2020 and the NH State Cancer Plan 2015-2020 have goals related to HPV vaccination for adolescent boys and girls. Both states also have organizations working to educate healthcare providers about the vaccine, as well as quality improvement initiatives. Our two states also have several key political and programmatic differences that impact HPV vaccination work, including differences in the public health infrastructure and tracking of immunization rates.

A previous, limited environmental scan of NH and VT was conducted by NCCC member [name] (PI) in collaboration with the Dartmouth Primary Care Cooperative Research Network (Dartmouth COOP) and the NH State Immunization Program several years ago. The National Cancer Institute has now awarded NCCC funding to conduct an in-depth environmental scan of HPV vaccine barriers, facilitators, activities, and opportunities in our catchment area. This will entail semi-structured interviews with key informants (e.g., public health professionals, healthcare providers), surveys with healthcare providers, a quality improvement project, online focus groups, surveys and message testing, and implementation/evaluation of a social media campaign about HPV vaccination. The key informant interviews (STUDY00030641), healthcare provider surveys (STUDY00030641), and quality improvement project (STUDY00030771) have been submitted to CPHS in separate applications. This application includes the online focus groups (Phase 1- IRB approved), message testing (Phase 2), and social media campaign (Phase 3- we will submit a modification before starting the campaign).

## 2. Objectives and Hypotheses

Related to the online focus groups, message testing, and social media components:

[figure not shown]
- 1) Identify HPV vaccine themes/messages/materials and measure their effectiveness to change parent attitudes and intentions to vaccinate their adolescent children;
- 2) Describe any differences in message/material effectiveness for parents residing in rural areas versus parents residing in urban areas
- 3) Launch a social media campaign with the most effective messages to improve parent attitudes.

[figure not shown]

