  - c. *Technical:* Access to all electronic files will be limited to CITI-trained research team members. Audio recordings of the focus groups will be destroyed after transcription. Electronic data will be stored on secure servers housed at DHMC with appropriate backup and will be shared across the research team using the research team's password-protected SharePoint site hosted by Dartmouth.

2. **Online message testing (Phase 2)** - Once the list of strong candidate themes is finalized, we will test the effects of those theme-relevant messages/materials on changing knowledge, attitudes, beliefs, and behavioral intentions of parents of children 9-14 years old living in New Hampshire and Vermont; (parents of any age child are invited to complete the survey as well, excluding questions related to vaccination history and intention to vaccinate). The message testing phase will involve pre/post-test designs. Prior to the message-testing phase (Phase 2), if needed, we will conduct anonymous online pilot surveys through Qualtrics. Prior to the message testing, this pilot test is to check the validity of each message (e.g., ensuring that the stimulus materials -campaign messages- are presented and perceived by audiences as we intended for positive effects).

To test the persuasion effects of candidate messages, we will measure an array of constructs in the pre-test stage (before exposure to materials/messages). A list of the candidate constructs that are critical in understanding message effectiveness include: prior knowledge, pre-existing attitudes, normative beliefs, response efficacy, and issue involvement. After finishing pre-test assessments, participants will be randomly assigned to one of the conditions and asked to read/review the stimulus material/message while experimentally controlling for high elaboration likelihood. After the message exposure step, participants will be asked to answer post-test survey measures, including: persuasiveness of the viewed message/material, attitude toward behavior promoted, response efficacy, behavioral intention, and normative belief assessment. A full list of finalized survey questionnaires and messages will be submitted in a future modification to this study, before the online message testing commences.

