- a) *Sample size and recruitment:* We expect to test a finalized set of messages, up to approximately 40 messages, with up to 30 people evaluating each message; as such, we will recruit maximum 1,200 people to complete message testing via various media recruitment and platforms (including Amazon Mechanical Turk and social media advertisements). For message testing

[figure not shown]
experiments, we implement two different cohort studies (Cohort 2A and 2B in Figure 1). Additional people will be screened for eligibility.

**Cohort Phase 1B:** Previously IRB-approved Cohort 1B is no longer part of this study design. We did not have large enough sample size to conduct a time-lag follow-up study, thus this Cohort 1B is removed from the project.

**Cohort Phase 2A:** We use paid advertisements on social media and MTurk to recruit residents in VT and NH. An external link to Qualtrics surveys will be embedded in the ads and in the MTurk posting. The message testing study will be held on Qualtrics. We will measure same constructs and examine an identical set of candidate messages across two cohorts. This cohort will not have a time-lag between pre- and post-assessments.

**Cohort Phase 2B:** We will implement the same message testing study and recruit participants in the US via Mturk and social media advertisements (e.g., Facebook ads). MTurk is an online labor market with more than 500,000 active members where requesters distribute small tasks, and workers complete the tasks for compensation as low as 1 cent in US dollars. More than 345,000 tasks are available on MTurk to anonymous workers to complete. The cohort will be invited to the same message-testing experiments with identical pre- and post-assessments used in Cohort 1B and Cohort 2A. The data from this national pool of participants will be used as reference points. This cohort does not have a time-lag between pre- and post-assessments.

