**b) Data collection methods:** After recruitment, we will screen participants for eligibility (criteria described below) with a Qualtrics-administered survey that asks the participant a series of questions that include the eligibility criteria as well as some dummy questions, to avoid deception on part of the prospective participant (see enclosed pre/post test survey). They will be asked to read the information sheet to proceed. Once they click the NEXT button to provide implicit consent to participate in the study, they will be asked to click on a link to the survey hosted on Qualtrics. They will be asked to answer pre-test questions. Cohort 1B will end survey and will be followed-up later for a random assignment for message exposure and post-assessments (for those who provide email address or MTurk worker ID number). After finishing pre-test, (without any time-lag), participants in Cohort 2A and 2B will be randomly assigned to one of the advertisement/message conditions in the following page. For message exposure, participants will be asked to carefully view the assigned message/material, and then answer a series of post-test questions. When participants finish the entire questionnaires, they will be debriefed and provided with useful resources about HPV. MTurk participants (Cohort 2B) will be asked to enter their worker ID (to verify their participation for compensation on Amazon Mechanical Turk). Eligible participants recruited from social media (Cohort 2A and 2B) who want to receive study compensation will have a chance to enter their contact email address for one of e-gift cards (to be sent to randomly selected participants). Eligible participants recruited from MTurk (Cohort 2A, and 2B) will be asked to provide their MTurk Worker ID number before being paid (amount described below). See enclosed document with examples of messages that participants could be exposed to/randomized to.

**c) Participant compensation:** Participants recruited from social media platforms (Cohort 2A and 2B) will have a chance to receive one of 50 e-gift cards worth up to \$10. Participants recruited through MTurk will be compensated as MTurk workers using their worker ID numbers. We estimate the screening questionnaire to take approximately up to 5 minutes and will compensate

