people up to \$0.50 for completing the screener. We estimate the actual survey/message testing to take about 15 minutes per participant. For those recruited through MTurk, based on typical MTurk payment amounts and based on [name] extensive experience with MTurk, we estimate each MTurk worker to receive up to \$1.50 for 15 minutes of message testing. This payment amount is in-line with typical payment amounts expected on MTurk (\$0.10/minute).

- d) *Eligibility:* Participants must be parents with at least one child who is 9-14 year old child living in New Hampshire or Vermont to complete the entire survey as part of Cohort 2A and in the US for Cohort 2B (parents with any age children are invited to complete the survey, excluding questions related to vaccination history and intention to vaccinate their 9-14 year old child/ren). The survey will contain a set of screening questions (as described earlier) to determine eligibility; geographic eligibility will be determined based on self-reported zip code/state and geo-targeting tools available on social media platforms.
- e) *Confidentiality and Protections:* Data will be collected online through Qualtrics. Any electronic data will be stored on password-protected computers and will only be viewable to CITI-trained research team members through Qualtrics portal and/or through this project's Dartmouth-hosted SharePoint site that is only accessible to the research team members via password. After data are no longer needed, they will be destroyed by the research team, and destruction will be confirmed by the information technology team at the Norris Cotton Cancer Center/Geisel School of Medicine. Further, participants will not be asked to reveal their names or social security numbers. We will ask demographic information, but these self-reported responses will be anonymized and paired with a random Study ID number. Responses will never be linked to any identifying information.

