#### 4. Analysis

**Describe any qualitative tests and measures as well as quantitative methods:**

1. **Online and local focus groups and message testing (Phases 1 & 2)-** Facebook comments, survey comments, and transcripts/audio files of the focus groups will be reviewed by the research team and coded for themes. We will also perform content and linguistic analyses. The self-reported survey measures will be examined for outliers and data skewness. Recording, transformation, or standardization will be made when necessary. We will conduct chi-square statistics for categorical variables and employ repeated GLM, ANOVA, ANCOVA, or regression statistics for continuous multivariate variables while controlling for relevant covariates. We will take structural equation modeling or path analyses to model persuasion pathways from message/ad exposure to changes in behavioral intentions to vaccinate. Based on persuasiveness scored rated for the HPV vaccine messages/ads, we will statistically test and select the

most highly-ranked messages/ads (best candidate messages/ads). These selected messages/ads will be used for the social media campaign.

2. **Social media campaign (Phase 3)-** We will measure message effectiveness by analyzing each message's effectiveness by assessing engagement data (provided by social media campaign metrics), and key constructs, including attitudes and intent to vaccinate (to be assessed via online survey embedded in the social media campaign messages). See enclosed survey; parents with children of any age are invited to complete all questions except for questions related to vaccination history and intention to vaccinate their 9-14 year old child/ren, which are limited to parents with 9-14 year old children. We will compare the differences between the two audience segments (rural vs. urban) or other subgroups of interest that emerge from the data. Although we do not solicit comments on Facebook, we expect that some Facebook users may leave comments/questions anyway; we will analyze the comments for themes and linguistic characteristics and compare between rural and urban audiences or by campaign themes (research team will de-identify all comments prior to analyses).

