We will compensate participants via the Amazon Mechanical Turk payment system daily. We will also monitor the recruitment status on MTurk while preventing duplicate participation. As needed, we will post additional ads on social media to help with recruitment and compensate participants who expressed their interest in receiving an e-gift card when the survey quota is met.

**Social media campaign (Phase 3)-** Our team will monitor the Facebook ads daily throughout the duration of the campaign; the daily monitoring will include an assessment of number of people reached by the ads, number of people completing the campaign evaluation survey, and number and content of comments left by Facebook users. Depending on the campaign reach and engagement, we will increase or decrease the amount of money allocated to each ad within Facebook. If a Facebook user leaves a comment or question on the ad, we will respond using the guidelines developed for our team (see enclosed document); the idea of generating user interaction guidelines was conceived by [name] as part of the research protocol section, and the guidelines were developed in consultation with the Marketing/Communications teams at Dartmouth-Hitchcock and at the Norris Cotton Cancer Center and have been developed using evidence-based information. Because the ads are being deployed using the Norris Cotton Cancer Center's Facebook page, the team will continue to consult with the Marketing/Communications teams as needed.

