**c. Define the target population:**

**1. Online focus groups/surveys (Phase 1)**- We will geo-target the Facebook ads to recruit from predominantly-rural ZIP codes and predominantly-urban ZIP codes (as defined by Rural-Urban Commuting Area (RUCA) Codes). Anyone viewing the ad will be eligible to leave comments. Those people interested in answering the private survey will need to confirm their ZIP code and that they have a child 9-14 years old for inclusion, as eligibility will be limited to parents with children 9-14 years old living in New Hampshire or Vermont.

**2. Local focus groups/surveys (Phase 1)**- Using the same RUCA definition as described above, we will identify several rural and urban communities in NH and VT for hosting the focus groups and recruiting the participants. Participants need to be parents of 9-14 year old children and live in VT or NH. We will screen prospective participants before the focus groups, asking:

Are you a parent?  
 Do you have at least one child between the ages of 9 and 14 years old?  
 Are you a resident of New Hampshire or Vermont?

**2. Online message testing (Phase 2)**- Participants must be parents with at least one child between the ages of 9-14 years old to complete all questions. They will be recruited from social media ads by targeting residents of NH or VT for eligibility (as determined by zip code), or via MTurk workers registered as parents in the US. For social media recruitment, we will only target our ads for

residents of New Hampshire and Vermont and will use Facebook ad targeting to target parents. The survey team will use a screening questionnaire to ensure eligibility (e.g., parents of 9-14 year-olds) for the full survey (parents of other age children are invited to complete the survey, with an exception of questions related to vaccination history and intent to vaccinate their 9-14 year old child/ren)

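### Objective 2 asks about rural-urban differences in message effectiveness, but the Phase 2 analysis, on the only data with described random assignment to messages, names no rural-urban term

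*Combined protocol and SAP*

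**What the plan says.** **Objective.** Section 2 lists three objectives for the focus groups, message testing and social media work together. The second is: "Describe any differences in message/material effectiveness for parents residing in rural areas versus parents residing in urban areas". It is not tied to one phase.

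**Phase 2 design.** Section 3, Online message testing (Phase 2), has pre-test measures, then assignment ("participants will be randomly assigned to one of the conditions and asked to read/review the stimulus material/message"), then post-test measures. The data collection paragraph repeats it: "participants in Cohort 2A and 2B will be randomly assigned to one of the advertisement/message conditions in the following page". Neither names a stratification factor. For Cohort 2A the text says "We use paid advertisements on social media and MTurk to recruit residents in VT and NH", without rural or urban strata. On location, the eligibility paragraph says "geographic eligibility will be determined based on self-reported zip code/state and geo-targeting tools available on social media platforms".

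**Phase 2 analysis.** Section 4, item 1, lists chi-square tests, GLM, ANOVA, ANCOVA or regression with unspecified covariates, and path models. Selection follows: "Based on persuasiveness scored rated for the HPV vaccine messages/ads, we will statistically test and select" the top-ranked messages. Rurality does not appear.

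**Phase 3.** Sections 3 and 4 plan a rural versus urban comparison of engagement, attitudes and intent for up to six messages delivered by geo-targeting. Section 5 adds that, depending on reach and engagement, "we will increase or decrease the amount of money allocated to each ad within Facebook".

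**The concern.** The study has one data set in which the message a parent sees is decided by chance and the same parent is measured before and after. The plan does not say that this data set will be used for Objective 2. The rural-urban answer is left to Phase 3, where three things weaken it:

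- Only messages that survived selection are seen, at most six of up to 40.
- Delivery is not described as random and spending per ad shifts during the campaign, so who sees which message may depend on how well it is already doing.
- The outcomes are aggregate engagement metrics and a survey completed by people who chose to click.

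Phase 3 can describe how two audiences responded to the final campaign. It is poorly placed to say whether the messages differ in their relative effect on rural and urban parents, and it says nothing about messages that were not selected. The covariate wording in Section 4 does not close the gap. Adjusting for rurality removes a main effect; only an interaction with message or theme estimates a difference in message effectiveness.

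**Working it through.** **1. The plan's own figure.** Section 9a gives 40 messages and 30 parents each: 40 × 30 = 1,200, which reproduces. Section 9b bases the 30 on experience. No alpha, power, SD or rural share is given, so there is no power calculation to reproduce and no allowance for a rural-urban split.

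**2. Where rurality appears.**

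| Component | Rural-urban element | Random assignment to message described |
|---|---|---|
| Phase 1 ads and survey | Recruitment stratified by RUCA | No |
| Phase 1 local focus groups | Up to five rural, up to five urban | No |
| Phase 2 message testing | None named in recruitment, allocation or analysis | Yes |
| Phase 3 campaign | Delivery and analysis by segment | No |

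**3. What Phase 2 could show.** Assumptions: two-sided 5%, 80% power, outcome in SD units, no gain from the pre-test covariate. The normal approximation is

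MDE = (1.96 + 0.84) × √(1/n_rural + 1/n_urban);

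the two-sample t value is slightly larger.

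*One message, all 30 raters with usable ZIP codes, half rural.* √(1/15 + 1/15) = 0.365. The MDE is 1.02 SD (normal) or 1.06 SD (t). The 95% half-width is 1.96 × 0.365 = 0.72 SD.

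*One theme.* Further assumptions: six themes, as in the Phase 1 ads, with parents spread evenly, so 1,200 / 6 = 200 per theme, or 100 if half of the 1,200 have NH or VT ZIP codes.

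| Share of 1,200 with NH/VT ZIP | Rural share | Rural vs urban per theme | MDE (t) |
|---|---|---|---|
| All | 50% | 100 vs 100 | 0.40 SD |
| All | 30% | 60 vs 140 | 0.43 SD |
| Half | 50% | 50 vs 50 | 0.57 SD |
| Half | 30% | 30 vs 70 | 0.62 SD |

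*Difference between two themes in their rural-urban contrast.* This interaction multiplies the MDE by √2. At half rural it is 0.56 SD with 100 per cell and 0.79 SD with 50 per cell (normal approximation).

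**4. What randomisation protects.** Parents are randomised to messages, not to places. Within rural parents, and within urban parents, comparisons between messages are protected. The rural-urban difference for one message or theme is observational in Phase 2, as it is in Phase 3. The advantage of Phase 2 is therefore in the interaction: whether the ordering of messages or themes differs between the two groups.

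**The case against.** The strongest reply is that Objective 2 is already served. It says only that differences will be described, it promises no test or power, and Phase 3 commits to a rural-urban comparison. This stands in part: a reader might infer that the objective has no analysis at all, or that low power contradicts it, and the documents support neither. What remains is that Phase 3 cannot replace the Phase 2 message comparison, for the reasons given above.

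Second, the moment for design changes seems to have passed. Section 3 (Phase 3) says strong messages have been identified from Phases 1 and 2, and Sections 6 and 7 say the campaign messages were already tested in a national sample. A reader might infer that stratified allocation, or a rural-urban review before selection, would still protect the choice of messages. On the documents' wording that is largely moot. With about 1.06 SD detectable per message, such a review would in any case have been a weak guide to choosing six from 40.

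Third, ZIP code is not assured for everyone. Eligibility refers to ZIP code or state; Section 9c links ZIP code to social media recruits in NH and VT, and describes MTurk recruits only as parents in the US. A reader might infer that all 1,200 can be classified, but that is not shown.

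Fourth, a reader might infer that selection used scores pooled across rural and urban parents. Section 4 does not say how scores were combined. Figure 1 and the questionnaires are not available here, so a stratum shown only there cannot be excluded.

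**Conclusion.** The concern holds as a gap in the analysis plan. Section 4 names no rural-urban term for the only phase with described random assignment to messages, although this is one of three stated objectives and location data exist for at least part of the sample.

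The gain from closing it is moderate. Theme-level rural-urban contrasts would detect about 0.40 to 0.62 SD. The lower end is a best case that needs all 1,200 parents to have NH or VT ZIP codes and half of them to be rural; the range also rests on six evenly filled themes, a number the documents give for Phase 1 but not for Phase 2. Per-message contrasts are too imprecise for more than display. Because residence is not randomised, the result is descriptive. A reader might infer that Phase 2 would yield a randomised rural-urban comparison; it would not.

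**What to change.** 1. For Phase 2 participants with a usable ZIP code, chiefly Cohort 2A, derive the RUCA class using the definition already adopted in Phase 1. State the number and share who cannot be classified.
2. In Section 4, item 1, add rurality and message-by-rurality (or theme-by-rurality) terms to the Phase 2 model. Use the pre-test score as covariate and shrink message effects, for example as random effects.
3. Report rural and urban estimates with 95% confidence intervals by theme and for the shortlisted messages. Label them descriptive and present them next to the Phase 3 comparison.
4. If any Phase 2 enrolment is still to come, balance message allocation within rural and urban strata in the survey software. Otherwise make only the analysis changes.

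The cost is ZIP-to-RUCA coding, a few lines of analysis text and one additional table. No extra participants are needed. Wide per-message intervals must be accepted and shown as such.
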